12.3.2 Analysis Plans

Patient demographics and baseline disease characteristics, including age, gender, medical history, and prior therapy, will be summarized using descriptive statistics. For continuous variables, descriptive statistics such as number, mean, standard deviation, standard error, median (range) etc. will be provided. For categorical variables, patient counts and percentages will be provided.

For all analyses, only eligible participants who received at least one dose of protocol treatment will be considered evaluable and included in the analyses. Eligible participants who did not receive any protocol treatment will be considered in-evaluable and excluded from all analyses.

PFS will be estimated using the product-limit method of Kaplan and Meier along with the Greenwood estimator of standard error. When there is no censoring in PFS prior to 18 months after the first dose of study treatment, the observed 18-month PFS will be compared to the baseline of 65% by one-sided exact test of binomial proportion. In case of censoring in PFS prior to 18 months after the first dose of study treatment (which are expected to be rare), the Kaplan-Meier estimate for 18-month PFS along with the Greenwood standard error estimator will be used for the testing of null hypothesis at 65%.

OS will be estimated using the product-limit method of Kaplan and Meier along with the Greenwood estimator of standard error. Cumulative incidence of relapse/progression and cumulative incidence of non-relapse mortality, as well as their confidence intervals will be estimated using competing risk methodology, treating the other event as a competing risk. Overall response rate will be estimated by the proportion of patients achieving either CR or PR among participants with measurable disease after ASCT, along with the exact binomial confidence interval.

Observed toxicities will be summarized by type (organ affected or laboratory determination such as absolute neutrophil count), severity (by NCI CTCAE v4.0 and nadir or maximum values for lab measures), date of onset, duration, reversibility, and attribution.

For the exploratory objects, descriptive statistics will be used to summarize the responses and outcomes for patients who receive protocol treatment past disease progression and the correlative study measures. For continuous variables, number, mean, standard deviation, standard error, median (range) etc., will be provided. For categorical variables, patient counts and percentages will be provided. Changes in these measures before, during, and after treatment (when measured) will also be summarized by descriptive statistics and tables/plots. Various statistical analyses will be used to explore the association between

these correlative endpoint measures (at different time points and the associated changes over time, when measured) with clinical outcomes such as PFS/OS and response. For the exploratory correlation of these endpoints with survival outcomes, survival analysis techniques such as Log rank test and Cox proportional hazard models will be considered. For the exploratory correlation of these endpoints with response, analyses comparing groups of participants defined by response may be conducted by various two sample tests such as two-sample t-test or Wilcoxon rank sum test for the continuous correlative endpoints, or Chi-square test/Fisher's exact test for the categorical correlative endpoints. Appropriate regression models will also be considered, such as logistic regression for analyses on response and Cox proportional hazards models for survival outcomes. All these analyses are exploratory in nature and no multiple comparison adjustments will be made in these exploratory analyses

12.3.3 *Toxicity Monitoring*

Close and continuous monitoring for toxicity will occur throughout the study duration per institutional standards. The COH DSMC will review the AE data quarterly. In the AETHERA trial [32], 56% of patients who received brentuximab vedotin experienced at least one Grade 3-4 adverse event, including 29% with Grade 3-4 neutropenia, 10% with Grade 3-4 peripheral sensory neuropathy, and 6% with Grade 3-4 peripheral motor neuropathy.

In this study, the total treatment number of cycles is reduced to 8 but the addition of nivolumab may introduce additional toxicities.

Given the prior toxicity experiences in AETHERA trial and the differences in treatment [32], in this study we will specifically monitor the occurrence of any "**unacceptable AE**". **Unacceptable AE** is defined as any of the following AEs that is at least **possibly attributed** to protocol therapy during treatment and safety follow-up:

- Any \geq Grade 3 immune-related AE
- Grade 3 fatigue or non-irAE skin toxicity that does not resolve within 7 days to \leq Grade 1/baseline
- Any other \geq Grade 3 non-hematologic non-irAE that does not improve within 3 days to \leq Grade 1/baseline as applicable with supportive care with the following **exception**:
 - \geq Grade 3 laboratory abnormality that is not clinically significant
- Grade 4 neutropenia that does not resolve to \leq Grade 2 within 3 days with supportive care (e.g. GCSF)
- Grade 3 or 4 thrombocytopenia with bleeding
- Any Grade 5 AE

This specific monitoring will be performed according to the rule below, which is based on the 50% quartile of the binomial distribution with an unacceptable toxicity rate of 33%.

- 3 or more patients with unacceptable toxicities when \leq 9 patients have been treated.
- 5 or more patients with unacceptable toxicities when \leq 16 patients have been treated.
- 8 or more patients with unacceptable toxicities when \leq 23 patients have been treated.
- 11 or more patients with unacceptable toxicities when \leq 33 patients have been treated.
- 15 or more patients with unacceptable toxicities when \leq 46 patients have been treated.

- 19 or more patients with unacceptable toxicities when ≤ 59 patients have been treated.

If the monitoring rule is met, the study PMT will review and assess the safety of the trial and submit a report outlining the findings and proposed action plans if any to the COH DSMC. The COH DSMC will review and make the decision to continue, modify, or permanently suspend accrual to the trial. At the end of the study with 59 evaluable participants, the 95% exact binomial confidence interval for the rate of such unacceptable AE will have a width of no more than 27%.

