- Explore the prognostic impact of and temporal dynamics of minimal residual disease (MRD) in the peripheral blood as assessed by the next-generation sequencing-based ClonoSEQ platform.

- Explore the prognostic impact of 9p24.1 abnormalities in tumor tissue assessed by FISH on outcomes after ASCT and nivolumab plus brentuximab vedotin post-ASCT consolidation therapy.
- Explore the relationship between immune cells and HRS in tumor samples by 6-color quantitative spatial image analysis using the Vectra system, and correlate with outcome after ASCT and nivolumab plus brentuximab vedotin post-ASCT consolidation therapy.
- Explore whether genetic alterations (e.g. gene expression profiles or genetic mutations) in HL tumor samples are associated with outcome after ASCT and nivolumab plus brentuximab vedotin post-ASCT consolidation therapy.

Evaluation Criteria and Endpoints:

- Response will be assessed per 2014 Lugano Classification.
- Clinical endpoints are as follows:

Endpoint	Patients	Definition
Progression-Free Survival (PFS)	Evaluable patients	Defined as the time from the first dose of study treatment to the first observation of disease relapse/progression or death from any cause, whichever occurs first.
Overall Survival (OS)	Evaluable patients	Defined as the time from the first dose of study treatment to death from any cause.
Cumulative Incidence of Non-Relapse Mortality (NRM)	Evaluable patients	Defined as the time from the first dose of study treatment to non-disease related death.
Cumulative Incidence of Relapse/Progression	Evaluable patients	Defined as the time from the first dose of study treatment to disease relapse/progression.
Overall response rate (ORR)	Evaluable patients with measurable disease post-ASCT	Proportion of patients achieving CR or PR

- Evaluable patients are defined as eligible participants who received at least one dose of the protocol treatment. Eligible participants who did not receive any protocol treatment will be considered in-evaluable, replaced, and excluded from all analyses.

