If the monitoring rule is met, the study PMT will review and assess the safety of the trial and submit a report outlining the findings and proposed action plans if any to the COH DSMC. The COH DSMC will review and make the decision to continue, modify, or permanently suspend accrual to the trial. At the end of the study with 59 evaluable participants, the 95% exact binomial confidence interval for the rate of such unacceptable AE will have a width of no more than 27%.

Eligibility Criteria

Inclusion Criteria

- Age: \geq 18 years
- ECOG performance status \leq 2
- Histologically confirmed diagnosis of classical Hodgkin lymphoma (excluding nodular lymphocyte predominant Hodgkin lymphoma) according to the WHO classification, with hematopathology review at the participating institution.
- Have high-risk relapsed or refractory Hodgkin lymphoma (HL), defined as at least one of the following:

- Primary refractory disease to front-line therapy.
- Relapse within 1 year of completing front-line therapy.
- Extranodal involvement at the time of pre-ASCT relapse.
- B symptoms at pre-ASCT relapse.
- More than one type of pre-ASCT salvage therapy required.
- Planning to receive or have received autologous stem cell transplantation (ASCT) per institutional standards as part of standard of care.
 - Pre-ASCT participants may consent but will not be eligible to begin treatment until after ASCT, and will have to fulfill all inclusion and exclusion criteria before starting protocol therapy.
 - All participants must initiate Day 1 of protocol therapy within 30-60 days post stem cell reinfusion. Study PI can grant exception for a patient to start as late as 75 days post stem cell reinfusion with a reasonable justification for delay (e.g. recovery from post-ASCT toxicity) and this will not be a protocol deviation, nor require an exception to be filed.
- Recovery from ASCT toxicity as defined as outpatient status , able to drink, eat normally, and do not need intravenous hydration prior to Day 1 of therapy
- Achieved at least stable disease to salvage treatment determined by PET/CT using 2014 Lugano classification prior to ASCT.
- Brentuximab vedotin naïve OR had at least stable disease by Lugano classification to prior brentuximab vedotin treatment
- ANC \geq 1000/mm³
- Platelets \geq 50,000/mm³
- Hemoglobin \geq 8 g/dL
- Total bilirubin \leq 1.5 x ULN OR 3 x ULN for Gilbert's disease
- AST and ALT \leq 2.5 x ULN

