7.7 Routine AE Reporting Guidelines

Routine AE reporting will occur via data entry into the study eCRF.

AEs reported through expedited processes (e.g., reported to the IRB, FDA, etc.) must also be reported in routine study data submissions.

AEs can be spontaneously reported or elicited during open-ended questioning, examination, or evaluation of a participant. (In order to prevent reporting bias, participants should not be questioned regarding the specific occurrence of one or more AEs.)

All AEs will be recorded from the initiation of protocol therapy through the follow-up period. The highest grade for any toxicity plus Grade 3 or 4 event for the same toxicity (if not the highest grade) will be reported during each cycle and during the safety follow-up period.

AE information recorded in the CRF include: Attribution to protocol therapy, grade and seriousness.

The collection of nonserious AE information should begin at initiation of protocol therapy up to a minimum of 100 days following the last dose of protocol therapy. Nonserious AEs should be followed to resolution or stabilization, or reported as SAEs if they become serious. Follow-up is also required for nonserious AEs that cause interruption or discontinuation of study drug and for those present at the end of study treatment as appropriate.

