11.1.3 Toxicity

Toxicity and adverse events will be recorded using the NCI CTCAE v 4.0. All toxicities/AEs will be recorded from the initiation of protocol therapy through the follow-up period. The highest grade for any toxicity plus Grade 3 or 4 event for the same toxicity (if not the highest grade) will be reported during each cycle and during the safety follow-up period.

Eligible participants who did not receive any protocol treatment will be considered in-evaluable, replaced, and excluded from all analyses on toxicity.

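### Section 12.3.2 limits every analysis, toxicity included, to eligible dosed participants and no all-dosed safety set is defined, so a dosed participant later found ineligible would be left out of the final safety results (minor)

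*Combined protocol and SAP*

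**What the plan says.** Section 12.3.2 (Analysis Plans) sets one population for everything: "For all analyses, only eligible participants who received at least one dose of protocol treatment will be considered evaluable and included in the analyses". Two conditions must both hold, eligibility and at least one dose. Later in the same section comes the safety summary, "Observed toxicities will be summarized by type (organ affected or laboratory determination such as absolute neutrophil count", with no population of its own.

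The synopsis (Evaluation Criteria and Endpoints) and Section 11.1.2 define the term in the same way: "Evaluable patients are defined as eligible participants who received at least one dose of the protocol treatment".

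Section 11.1.3 (Toxicity) speaks only of people who were never dosed: "Eligible participants who did not receive any protocol treatment will be considered in-evaluable, replaced, and excluded from all analyses on toxicity". It does not mention someone who was dosed and later found ineligible.

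Section 12.3.3 (Toxicity Monitoring) uses two terms. The last tier of the monitoring rule applies when up to "59 patients have been treated". The closing precision statement is for evaluable participants: "At the end of the study with 59 evaluable participants, the 95% exact binomial confidence interval for the rate of such unacceptable AE". The synopsis repeats that statement and gives the limit on the interval in percent: "the rate of such unacceptable AE will have a width of no more than 27".

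Collection is wider than analysis. Under Section 7.7, "All AEs will be recorded from the initiation of protocol therapy through the follow-up period", with no eligibility condition.

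**The concern.** Safety and tolerability is a secondary objective (Section 1.2), and Section 12.3.3 itself notes that adding nivolumab may bring further toxicities. Everyone exposed to the combination is informative about its safety, whether or not an entry criterion was in fact met. An eligibility condition may be defensible for the PFS test, where the aim is a comparison with a historical rate in a defined population. It does not suit AE reporting.

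If 12.3.2 is followed as written, the AEs of a dosed but ineligible participant are collected and seen by the DSMC, yet are missing from the final AE tables and from the final unacceptable-AE rate. The effect on a percentage is slight. The effect on a rare serious event can be complete: one treatment-related death could be absent from the reported results.

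**Working it through.** **1. The plan's own figures.** Inputs from Section 12.3.3: n = 59, exact (Clopper-Pearson) 95% interval, width no more than 27%, and tiers of 3, 5, 8, 11, 15 and 19 patients at 9, 16, 23, 33, 46 and 59 treated, described as the 50% point of a binomial distribution with rate 33%.

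- Interval for x events in n: lower limit = Beta quantile(0.025; x, n − x + 1), upper limit = Beta quantile(0.975; x + 1, n − x). Over all x at n = 59 the greatest width is 26.6% (x = 30), which agrees with the stated limit.
- The medians of Binomial(n, 0.33) at the six values of n are 3, 5, 8, 11, 15 and 19. All six tiers reproduce.

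The plan's numbers are therefore correct; the point concerns the population only.

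**2. Who is covered by each sentence.**

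| Participant | 12.3.2, all analyses | 11.1.3, toxicity |
|---|---|---|
| Eligible, dosed | included | not excluded |
| Eligible, never dosed | excluded | excluded |
| Dosed, later found ineligible | excluded by the word *only* | not mentioned |

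Nothing in the documents brings the third row back in for safety.

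**3. Effect of one omitted participant on the unacceptable-AE rate.** The documents give no frequency of ineligible dosing, so the effect is shown per case, near the plan's last tier of 19 events in 59. Both accrual outcomes are shown, because the replacement sentence names only never-dosed participants.

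- With an event, accrual continuing to 59 eligible dosed: 20/60 = 33.3% becomes 19/59 = 32.2%, a fall of 1.1 points.
- With an event, accrual not continuing: 19/59 = 32.2% becomes 18/58 = 31.0%, a fall of 1.2 points.
- Without an event, accrual continuing: 19/60 = 31.7% becomes 19/59 = 32.2%, a rise of 0.5 points.
- Without an event, accrual not continuing: 19/59 = 32.2% becomes 19/58 = 32.8%, a rise of 0.6 points.

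For comparison, the exact 95% interval is 21.7–46.7% at 20/60 and 20.6–45.6% at 19/59, each 25.0 points wide.

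Assuming instead one, two or three such participants out of 59 dosed, with 19 events in all and no further accrual: if all of them had events, the reported rate is 18/58 = 31.0%, 17/57 = 29.8% or 16/56 = 28.6%. If none did, it is 19/58 = 32.8%, 19/57 = 33.3% or 19/56 = 33.9%.

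**4. Effect on a single rare event.** One Grade 5 AE among 60 dosed is 1/60 = 1.7% (95% CI 0.04–8.9%). If that participant is the ineligible one, the report shows 0/59 (95% CI 0–6.1%).

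**5. What an all-dosed set would do to the stated figures.** The number dosed may pass 59, up to the accrual maximum of 65. The greatest exact interval width is 26.6% at 59, 26.4% at 60 and 25.3% at 65, so the 27% statement still holds. The listed tiers stop at 59. On their existing basis, the median of Binomial(n, 0.33) is 20 for n = 60 to 62 and 21 for n = 63 to 65.

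**The case against.** The best reply is that the plan never meant to exclude anyone who was dosed. Every sentence that says who is left out names only the never-dosed. In 12.3.2 the restriction is followed directly by the sentence on eligible participants who received nothing, so *eligible and dosed* may have been meant only as their counterpart. Section 11.1.3, the one passage specific to toxicity, removes only the never-dosed, and Section 12.2 gives the target as 59 with at least one dose, without the word *eligible*. Eligibility is checked centrally against source documents before registration (Section 4.2.3), and those who consent before transplant must meet all criteria again before starting therapy (Section 3.1). A death on treatment would still be a serious AE, reported within 24 hours (Table 7.8.2) and open to the quarterly DSMC review (Section 15.7).

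Much of this stands. It shows that cases should be few, that an all-dosed toxicity set may well have been intended, and that oversight during the trial is not weakened. It does not change the text: 12.3.2 says *only* and *all analyses*, and no passage includes a dosed participant found ineligible. A check at registration also cannot catch facts that surface later. Section 14.3 provides for deviations discovered after they occur, though it does not mention eligibility.

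A reader might also infer that the monitoring rule and the final rate use different denominators, since one says *treated* and the other *evaluable*. The documents do not establish this. Section 12.3.3 uses 59 for both, which suggests that one group was in mind, and the *all analyses* wording could be read to cover the monitoring count as well. The precision sentence is also a planning statement at the intended sample size. The relation between the two terms is ambiguous; on either reading the final tables omit the participant.

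**Conclusion.** The point holds as a gap in population definition, of minor severity. Followed literally, 12.3.2 drops a dosed participant later found ineligible from the final AE tables and the final unacceptable-AE rate. Per case, the rate moves by about 0.5 to 1.2 points, small beside an interval about 25 points wide. The consequence that matters is the possible loss of a single serious event from the final report.

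This rests on the literal wording of 12.3.2 and on at least one such participant occurring, for which the documents give no rate. It affects final reporting only: AE collection, expedited reporting, DSMC review, the primary endpoint, power and the 45/59 rule are untouched. It would be wrong to conclude that the plan's toxicity figures are in error, since all of them reproduce, or that the DSMC would be working from incomplete data.

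**What to change.** In Sections 11.1.3 and 12.3.2, and in the last sentence of 12.3.3 with its copy in the synopsis, define the safety set as every participant who received at least one dose of either agent, regardless of eligibility. Use it for all AE summaries, for the final unacceptable-AE rate with its exact interval, and for the monitoring count. This also settles how *treated* and *evaluable* relate.

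Because the number dosed may then exceed 59, add one sentence saying that the monitoring rule continues on its existing binomial-median basis above 59. That basis gives 20 at 60 to 62 treated and 21 at 63 to 65.

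Leave the eligible-and-dosed set for PFS and the 45/59 rule unchanged. Section 12.2 need not be reworded for this point.

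The cost is a few sentences. No new data are needed, since AEs are already recorded for everyone from the start of therapy. The existing six tiers and the 27% width statement stand.
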